9.9. Limitations of the Research Methods

As this study aims at collecting real-world evidence, some limitations common to non-interventional studies apply. In addition to this, the following aspects need to be considered:

Although sites will be selected to promote representativeness for the respective country or region as much as possible, sites also need to have sufficient interest and capacities to participate in the registry.

Although eligible patients should be consecutively enrolled at a site, it needs to be considered, that patients need to give their informed consent for their medical records to be extracted. This might hamper consecutive enrolment at a site.

To allow for demonstrating representativeness of edoxaban patients included into the trial, an enrolment log will have to be filled by the sites, where all patients treated with edoxaban at the site at discretion of the physician need to be listed and the reason to participate or not to participate needs to be documented.

No explicit non-eligibility criteria are defined to avoid selection of patients and thus violation of the "real-life" principle.

However, as data collected in the study is part of routine medical practice and not collected for the purpose of the study, the extent of available information and the classification/description of medical data and procedures could vary.

Concerning the evaluation of effectiveness of the educational program, it could be noted that participation in a survey may not be representative of the target users given that participation is more likely amongst engaged healthcare professionals and/or more motivated or educated individuals.

10. PROTECTION OF HUMAN SUBJECTS

To ensure the quality and integrity of research, this study will be conducted under the Guidelines for Good Pharmacovigilance Practices (GVPs) and Good Pharmacoepidemiology Practices (GPPs) issued by the International Society for Pharmacoepidemiology (ISPE), the Declaration of Helsinki and its amendments, and any applicable national guidelines.

10.1. Review by Ethics Committees/Competent Authorities (CAs)

Notification to or approval by IECs and CAs or other organizations will be performed as required by national regulations in the participating countries before commencement of enrolment at a study site.

10.2. Insurance and Liability

All treatments of patients included in this DUS are local standard of care and occur as part of the daily routine practice. The registry is non-interventional and does not foresee any change from treatment nor additional examinations apart from the standard of care. Insurance coverage will only be provided with regards to the product liability. A specific patient's insurance for DUS is not necessary (if not in contradiction with specific legal requirements in the country of conduct).

10.3. Patient Information, Informed Consent

Written Informed Consent will be obtained from all patients in informed consent forms (ICFs) in order to agree his/her patient source data are being transferred into an eCRF and are evaluated and analysed for scientific purposes.

10.4. Data Protection

The patients' privacy will be kept according to the requirements of Directive 95/46 EC and national legislation for data protection. Data will be collected in a pseudonymous way. A patient identification number (ID) assigned to each patient will be used in lieu of the patient's name to protect the patient's identity when reporting any study-related data.

Only authorised personnel as hospital/site staff, representatives of the sponsor and CRO, and CAs should have access to personalised patient data e.g. in original source documents (medical records). The patient will agree to this by signing a respective statement on the ICF.

10.5. Numbering and Identification of Patients

A patient ID will be assigned to each patient when reporting data in the eCRF or on the paper CRF. The patient ID will consist of the country code, followed by a three digit site number and the consecutive patient number (e.g. UK-001-001). Medical record number or other local reference identifiers are not collected.

At each site a patient ID list will be kept linking the ID to the patient's identity.

10.6. Assessments

The investigators or the data retriever will be instructed regarding the correct documentation of the required information to be captured for each patient in the eCRF. These data are available as part of the routine treatment.

11. MANAGEMENT AND REPORTING OF ADVERSE DRUG REACTIONS (ADR)

All adverse drug reactions that are judged by the investigator as related to edoxaban need to be reported according to the national requirements and local laws. The documentation and reporting follows the Guideline on Good Pharmacovigilance Practices (GVP Module VI).

11.1. **Definitions**

Adverse Drug Reaction (ADR)

A response to a medicinal product which is noxious and unintended and which occurs at doses normally used in man for the prophylaxis, diagnosis or therapy of disease or for the restoration, correction or modification of physiological function.

Response in this context means that a causal relationship between a medicinal product and an adverse event is at least a reasonable possibility.

Adverse reaction also includes adverse clinical consequences associated with use of the product outside the terms of the Summary of Product Characteristics or other conditions laid down for the marketing and use of the product (including prescribed doses higher than those recommended, overdoses or abuse).

Serious Adverse Drug Reaction

Serious adverse reaction means an adverse reaction which results in:

- Death
- Is life-threatening
- Requires inpatient hospitalisation or prolongation of existing hospitalisation
- Results in persistent or significant disability or incapacity, or
- Is a congenital anomaly/birth defect.

Life threatening in this context refers to a reaction in which the patient was at risk of death at the time of the reaction; it does not refer to a reaction that hypothetically might have caused death if more severe.

Medical and scientific judgement should be exercised in deciding whether other situations should be considered serious reactions, such as important medical events that might not be immediately life threatening or result in death or hospitalisation but might jeopardise the patient or might require intervention to prevent one of the other outcomes listed above. Examples of such events are intensive treatment in an emergency room or at home for allergic bronchospasm, blood dyscrasia or convulsions that do not result in hospitalisation or development of dependency or abuse.

11.2. Reporting of suspected ADRs by the Investigator

All Edoxaban related adverse drug reactions need to be reported by the site to the pharmacovigilance department of the sponsor as spontaneous ADR reports. The study specific ADR reporting form has to be sent to the respective Daiichi Sankyo affiliate in the country where the site is located and will then be forwarded to the sponsor (Daiichi Sankyo Europe GmbH, Clinical Safety & Pharmacovigilance Department, [name], 81379 Munich, Germany). The sponsor will process all the ADR details in line with the requirements for spontaneous ADR reporting and in accordance with the Guideline on Good Pharmacovigilance Practices (GVP).

In addition, the investigator has to confirm in the eCRF whether or not an ADR has been reported.

12. PLANS FOR DISSEMINATING AND COMMUNICATING STUDY RESULTS

12.1. Progress Reports

As already mentioned in section 11 Daiichi Sankyo will summarise relevant safety information or information with potential impact in the benefit-risk assessment (if any) in Periodic Safety Update Reports.

12.2. Annual/Interim Analyses and Reporting

The interim report will be prepared after the completion of data collection in the first wave countries. The interim report will be provided in the third Quarter 2017.

13. DOCUMENTATION AND ARCHIVING

The Sponsor is responsible for archiving study specific documentation (Observational plan, potential amendments, Final Report and Database) for at least ten years. Archived data may be held on electronic record, provided that a back-up exists and that hard copies can be obtained, if required.

The investigator is responsible for archiving the patient ID list, all signed ICFs and his/her contract for at least ten years and in accordance with local legislation.

Physicians are obliged to keep patient files according to national requirements.

14. LEGAL REQUIREMENTS

This DUS fulfils the requirements of the Directive 2001/83 EC, Module VIII of GVP, Directive 95/46 EC, the Declaration of Helsinki and will be conducted in accordance with the respective Standard Operating Procedures (SOP) of DSE.

14.1. Reimbursement

Compensation according to local regulations and to the time spent to inform patients and to document patient data will be paid two times a year if not specified otherwise in the site contract.

Investigator fees per patient:

will account for the time spent related to the study and is estimated to 7.5hours per patient. The fees are split to different study personals (investigators, study coordinators, study nurses) involved in the DUS. The number of hours was calculated taking into account:

- Repeated time by patient (information and consent discussion, extraction of
 patients data, data completed within the secured eCRF, edit checks and quality of
 data and regular monitoring
- Set up of the study (site initiation Visits, eCRF training, initial screening of potential eligible patients, Lixiana ® Survey questionnaires (2)).

The investigator fees will be calculated taking the Fair Market Value benchmarking priced within the industry in considerations.

14.2. Registration

In accordance with the 2010 EU pharmacovigilance legislation, information about this DUS will be entered into the publically available European Network of Centres for Pharmacoepidemiology and Pharmacovigilance (ENCePP) E-Register of Studies. The study protocol will be entered into the register before the start of data collection. Updates to the study protocol in case of substantial amendments, progress reports where applicable, and the final study report will also be entered in the register.

15. FINAL REPORT

A final report will be presented by end of the second Quarter 2019, latest 6 months after data base lock. The final report will encompass all planned analyses, including a description of the complete study population (in all countries), as described above and in the SAP.

16. PUBLICATION

In order to protect confidential information and/or the interests of DSE, all publications (manuscripts and congress presentations) or announcements originating from this research are governed the Sponsor.

17. PREMATURE TERMINATION OF THE NIS/REGISTRY

The physician may withdraw his/her participation in this registry at any time. In the case of a premature termination of the entire DUS by the sponsor, the project leader has to inform all participating sites, IECs, and CAs.

APPENDIX 1. ENCEPP CHECKLIST

Doc.Ref. EMA/540136/2009

ENCePP Checklist for Study Protocols (Revision 2, amended)

Adopted by the ENCePP Steering Group on 14/01/2013

The European Network of Centres for Pharmacoepidemiology and Pharmacovigilance (ENCePP) welcomes innovative designs and new methods of research. This Checklist has been developed by ENCePP to stimulate consideration of important principles when designing and writing a pharmacoepidemiological or pharmacovigilance study protocol. The Checklist is intended to promote the quality of such studies, not their uniformity. The user is also referred to the ENCePP Guide on Methodological Standards in Pharmacoepidemiology which reviews and gives direct electronic access to guidance for research in pharmacoepidemiology and pharmacovigilance.

For each question of the Checklist, the investigator should indicate whether or not it has been addressed in the study protocol. If the answer is "Yes", the page number(s) of the protocol where this issue has been discussed should be specified. It is possible that some questions do not apply to a particular study (for example in the case of an innovative study design). In this case, the answer 'N/A' (Not Applicable) can be checked and the "Comments" field included for each section should be used to explain why. The "Comments" field can also be used to elaborate on a "No" answer.

This Checklist should be included as an Annex by marketing authorisation holders when submitting the protocol of a non-interventional post-authorisation safety study (PASS) to a regulatory authority (see the Guidance on the format and content of the protocol of non-interventional post-authorisation safety studies). Note, the Checklist is a supporting document and does not replace the format of the protocol for PASS as recommended in the Guidance and Module VIII of the Good pharmacovigilance practices (GVP).

Study title:

Edoxaban prescription patterns in Europe: a retrospective drug utilisation chart review study

Study reference number:

DSE-EDO-01-14-EU

Sect	Section 1:		No	N/A	Page Number(s)
1.1	Does the protocol specify timelines for				
	1.1.1 Start of data collection ²	\boxtimes			22
	1.1.2 End of data collection ³				22
	1.1.3 Study progress report(s)		\boxtimes		
	1.1.4 Interim progress report(s)		\boxtimes		
	1.1.5 Registration in the EU PAS register		\boxtimes		
	1.1.6 Final report of study results.				22
Com	ments:	•	•	•	
a		T 7	.	NT/ A	D
Sect	tion 2: Research question	Yes	No	N/A	Page Number(s)
2.1	Does the formulation of the research question and objectives clearly explain:				
	2.1.1 Why the study is conducted? (e.g. to address an important public health concern, a risk identified in the				25
	risk management plan, an emerging safety issue)		$ \Box$	Ιп	25-26
	2.1.2 The objective(s) of the study?				
	2.1.3 The target population? (i.e. population or subgroup to whom the study results are intended to be generalised)				28
	2.1.4 Which formal hypothesis(-es) is (are) to be				
	tested?	$ \Box $			
	2.1.5 If applicable, that there is no a priori hypothesis?				
Com	ments:				
Not	applicable.				
Sect	tion 3: Study design	Yes	No	N/A	Page Number(s)
3.1	Is the study design described? (e.g. cohort, case- control, randomised controlled trial, new or alternative design)	\boxtimes			27-28

 $^{^{2}}$ Date from which information on the first study is first recorded in the study dataset or, in the case of secondary use of data, the date from which data extraction starts.

³ Date from which the analytical dataset is completely available.

Sec	tion 3: Study design	Yes	No	N/A	Page Number(s)
3.2	Does the protocol specify the primary and secondary (if applicable) endpoint(s) to be investigated?				
3.3	Does the protocol describe the measure(s) of effect? (e.g. relative risk, odds ratio, deaths per 1000 person-years, absolute risk, excess risk, incidence rate ratio, hazard ratio, number needed to harm (NNH) per year)				
Com	ments:				
Des	scriptive analysis will be performed.				
Sec	tion 4: Source and study populations	Yes	No	N/A	Page Number(s)
4.1	Is the source population described?				28
4.2	Is the planned study population defined in terms of: 4.2.1 Study time period? 4.2.2 Age and sex? 4.2.3 Country of origin?				29 30
	4.2.4 Disease/indication?4.2.5 Co-morbidity?4.2.6 Seasonality?				30
4.3	Does the protocol define how the study population will be sampled from the source population? (e.g. event or inclusion/exclusion criteria)	\boxtimes			33
Com	ments:			·I	1
Not	t Applicable.				
Sec	tion 5: Exposure definition and measurement	Yes	No	N/A	Page Number(s)
5.1	Does the protocol describe how exposure is defined and measured? (e.g. operational details for defining and categorising exposure)				31
5.2	Does the protocol discuss the validity of exposure measurement? (e.g. precision, accuracy, prospective ascertainment, exposure information recorded before the outcome occurred, use of validation sub-study)			\boxtimes	
5.3	Is exposure classified according to time windows?				31

Sec	tion 5: Exposure definition and measurement	Yes	No	N/A	Page Number(s)
5.4	Is exposure classified based on biological mechanism of action and taking into account the pharmacokinetics and pharmacodynamics of the drug?				
5.5	Does the protocol specify whether a dose-dependent or duration-dependent response is measured?			\boxtimes	
Com	ments:			•	
Elig	gible patients are those prescribed edoxaban since its la	unch.			
-					, 
Sec	tion 6: Endpoint definition and measurement	Yes	No	N/A	Page Number(s)
6.1	Does the protocol describe how the endpoints are defined and measured?				
6.2	Does the protocol discuss the validity of endpoint measurement? (e.g. precision, accuracy, sensitivity, specificity, positive predictive value, prospective or retrospective ascertainment, use of validation sub-study)				
Com	ments:		ı	I	1
Not	applicable.				
Sec	tion 7: Confounders and effect modifiers	Yes	No	N/A	Page Number(s)
7.1	Does the protocol address known confounders? (e.g. collection of data on known confounders, methods of controlling for known confounders)			\boxtimes	
7.2	Does the protocol address known effect modifiers? (e.g. collection of data on known effect modifiers, anticipated direction of effect)			\boxtimes	
Com	ments:				
Not	applicable.				
Sec	tion 8: Data sources	Yes	No	N/A	Page Number(s)
8.1	Does the protocol describe the data source(s) used in the study for the ascertainment of:				
	8.1.1 Exposure? (e.g. pharmacy dispensing, general practice prescribing, claims data, self-report, face-to-face interview, etc.)				30-32

Section 8: Data sources			No	N/A	Page Number(s)
	8.1.2 Endpoints? (e.g. clinical records, laboratory markers or values, claims data, self-report, patient interview including scales and questionnaires, vital			\boxtimes	
	statistics, etc.) 8.1.3 Covariates?				33-36
8.2	Does the protocol describe the information available from the data source(s) on:				
	8.2.1 Exposure? (e.g. date of dispensing, drug quantity, dose, number of days of supply prescription, daily dosage, prescriber)				
	8.2.2 Endpoints? (e.g. date of occurrence, multiple event, severity measures related to event)			\boxtimes	
	8.2.3 Covariates? (e.g. age, sex, clinical and drug use history, co-morbidity, co-medications, life style, etc.)		\boxtimes		
8.3	Is a coding system described for:				
	8.3.1 Diseases? (e.g. International Classification of Diseases (ICD)-10)		\boxtimes		
	8.3.2 Endpoints? (e.g. Medical Dictionary for Regulatory Activities (MedDRA) for adverse events)		\boxtimes		
	8.3.3 Exposure? (e.g. WHO Drug Dictionary, Anatomical Therapeutic Chemical (ATC)Classification System)				
8.4	Is the linkage method between data sources described? (e.g. based on a unique identifier or other)		\boxtimes		
Com	ments:	•	•		
It is	not know yet what information will effectively be available.	ilable o	n the r	nedical	records.
Sect	tion 9: Study size and power	Yes	No	N/A	Page Number(s)
9.1	Is sample size and/or statistical power calculated?	\boxtimes			33-36
Com	ments:				
Not	applicable.				
Sect	tion 10: Analysis plan	Yes	No	N/A	Page Number(s)
10.1	Does the plan include measurement of excess risks?			\boxtimes	

Secti	on 10: Analysis plan	Yes	No	N/A	Page Number(s)
10.2	Is the choice of statistical techniques described?				33-36
10.3	Are descriptive analyses included?	\boxtimes			33-36
10.4	Are stratified analyses included?	\boxtimes			33-36
10.5	Does the plan describe methods for adjusting for confounding?		\boxtimes		
10.6	Does the plan describe methods addressing effect modification?		\boxtimes		
Comm	ents:				
The .	Analysis Plan will be further developed in a specific S	tatistic	al Ana	lysis Pla	an.
Secti	on 11: Data management and quality control	Yes	No	N/A	Page
					Number(s)
11.1	Is information provided on the management of missing data?				33-36
11.2	Does the protocol provide information on data storage? (e.g. software and IT environment, database maintenance and anti-fraud protection, archiving)				
11.3	Are methods of quality assurance described?	\boxtimes			38-39
11.4	Does the protocol describe possible quality issues related to the data source(s)?				39
11.5	Is there a system in place for independent review of study results?				38
Comm	ents:				
Not a	Applicable.				
Secti	on 12: Limitations	Yes	No	N/A	Page Number(s)
12.1	Does the protocol discuss:				
	12.1.1 Selection biases?	\boxtimes			39
	12.1.2 Information biases?(e.g. anticipated direction and magnitude of such biases, validation sub-study, use of validation and external data, analytical methods)				39
12.2	Does the protocol discuss study feasibility? (e.g. sample size, anticipated exposure, duration of follow-up				

in a cohort study, patient recruitment)

Secti	on 12: Limitations	Yes	No	N/A	Page Number(s)
12.3	Does the protocol address other limitations?	\boxtimes			38
Comm	ents:	•			•
Not A	Applicable.				
Secti	on 13: Ethical issues	Yes	No	N/A	Page Number(s)
13.1	Have requirements of Ethics Committee/Institutional Review Board approval been described?				41
13.2	Has any outcome of an ethical review procedure been addressed?				
13.3	Have data protection requirements been described?				41
Comm	ents:				•
Not A	Applicable.				
Secti	on 14: Amendments and deviations	Yes	No	N/A	Page Number(s)
14.1	Does the protocol include a section to document future amendments and deviations?				12
Comm	ents:	•			•
Not A	Applicable.				
Secti	on 15: Plans for communication of study results	Yes	No	N/A	Page Number(s)
15.1	Are plans described for communicating study results (e.g. to regulatory authorities)?				45
15.2	Are plans described for disseminating study results externally, including publication?				49
Comm	ents: Applicable.				

Name of the main author of the protocol:	_
Date: 18/05/2016	
Signature:	

APPENDIX 2. LIXIANA® - SURVEY QUESTIONNAIRE

Thank you for participating in this voluntary survey to monitor the use of edoxaban in Europe. Please answer each question/statement as honestly as possible. You will not be individually assessed as results will be reported in aggregate form only and not linked to any personal identifier. All information collected during the course of the survey will be kept strictly confidential.

Part I – Edoxaban utilisation

rt I	- Euoxana	in utilisation
1.		g the indications for which Lixiana is approved in the European Union icate if the following sentences are true (T) or false (F):
		Lixiana is indicated in the prevention of stroke in adult patients with nonvavular atrial fibrillation with or without risks factors Lixiana is indicated in the prevention of systemic embolism in adult
	0.	patients with nonvalvular atrial fibrillation with one or more risk factors
	c.	Lixiana is indicated in the treatment of deep vein thrombosis (DVT) and pulmonary embolism (PE) in adults
	d.	Lixiana is not indicated in the prevention of recurrent DVT and PE in adults
	e.	Lixiana is indicated in the prevention of VTE in subjects undergoing orthopaedic surgery
	f.	Lixiana is indicated in the prevention of atherothrombotic events after acute coronary syndrome
2.		g the recommended dosing of Lixiana, please indicate if the following are True (T) or false (F):
	a.	In patients with mild to moderate hepatic impairment, the recommended daily dose is of 30mg
	b.	In patients with normal renal and hepatic function, the recommended daily dose is of 60mg
	c.	In patients with moderate to severe renal impairment as defined by a creatinine clearance between 15 and 50 mL/min, the recommended daily dose is of 30mg
	d.	Lixiana has to be taken outside of meals
	e.	The duration of treatment with Lixiana is well defined and independent of transient or permanent risk factors
	f.	Co-administration with cyclosporine does not require any adjustment in the dose of Lixiana

- 3. Lixiana is contraindicated or not recommended in the following special patient populations (please select all that apply):
 - a. Severe hepatic impairment
 - b. Elevated liver enzymes ALT/AST 2x ULN
 - c. Hepatic disease associated with coagulopathy and clinically relevant bleeding
 - d. In co-administration with low dose ASA ($\leq 100 \text{mg/day}$)
 - e. Uncontrolled severe hypertension
 - f. Patients with a body weight $\leq 60 \text{ Kg}$
- 4. When initiating treatment with Lixiana, an initial course of heparin for at least 5 days prior to treatment with Lixiana must be observed (please select the correct answer):
 - a. In the treatment of patients with DVT and PE
 - b. In the prevention of stroke and systemic embolism in patients with NVAF
 - c. In both the treatment of DVT and PE patients, and prevention of stroke and systemic embolism in patients with NVAF
- 5. In the occurrence of a missed dose, the patient should be instructed to take it immediately even if it means to double the prescribed dose on the same day. Please indicate if the sentence is:
 - a. True
 - b. False
 - c. I don't know
- 6. When switching patients to Lixiana from non-Vitamin K antagonist oral anticoagulants, the non-VKA must be discontinued and Lixiana initiated at the time of the non-VKA next dose. Please indicate if the sentence is:
 - a. True
 - b. False
 - c. I don't know
- 7. When switching patients to Lixiana from Vitamin K antagonist anticoagulants, the INR must be ≤2.5 after discontinuing the VKA and before initiating Lixiana. Please indicate if the sentence is:
 - a. True
 - b. False
 - c. I don't know

- 8. When switching patients from Lixiana to warfarin, the initial dose of Lixiana remains the same during concomitant use. Please indicate if the sentence is:
 - a. True
 - b. False
 - c. I don't know
- 9. When switching patients from Lixiana to warfarin, the INR should be measured 3 times (please selected the correct answer):
 - a. Just after taking the daily dose of Lixiana
 - b. Just prior to taking the daily dose of Lixiana
 - c. One time just before the daily dose of Lixiana, a second time 1h after the daily dose of Lixiana and a third time 2 hours after the daily dose of Lixiana
- 10. When switching patients to Lixiana from parenteral anticoagulant therapy, or from parenteral anticoagulant therapy to Lixiana, the initial therapy must be always discontinued before initiating the second. Please indicate if the sentence is:
 - a. True
 - b. False
 - c. I don't know
- 11. Lixiana must be initiated immediately after discontinuing the continuously administered parenteral anticoagulant therapy. Please indicate if the sentence is:
 - a. True
 - b. False
 - c. I don't know
- 12. Concerning the perioperative management of patients under treatment with Lixiana (please select the correct answer):
 - a. Lixiana does not need to be stopped before a surgical intervention or other invasive procedure
 - b. Lixiana should be stopped at least 12 hours before a surgical intervention or other invasive procedure
 - c. Lixiana should be stopped at least 24 hours before a surgical intervention or other invasive procedure
 - d. I don't know
- 13. In case of overdose with Lixiana (please select the correct answer):
 - a. The patient must be given an antidote during the first 2 hours

- b. There is no antidote available, early administration of activated charcoal may be considered to reduce absorption
- c. Haemodialysis must be considered
- d. I don't know
- 14. In the management of bleeding complications treatment with Lixiana must be delayed or discontinued
 - a. True
 - b. False
 - c. I don't know
- 15. When taking Lixiana, routine coagulation tests include: INR, PT and aPTT. Please indicate if the sentence is:
 - a. True
 - b. False
 - c. I don't know

Part II – General questions

- 16. Are you aware of the Prescriber's Guide for Lixiana?
 - Yes
 - No
- 17. Have you received the Prescriber's Guide for Lixiana?
 - Yes
 - No
- 18. You received the Prescriber's Guide:
 - Before prescribing Lixiana for the first time
 - After prescribing Lixiana for the first time
- 19. Have you read the Prescriber's Guide?
 - Yes, completely
 - Yes, partially
 - No

If not:

- 20. You have not read the Prescriber's Guide, please select the most relevant reason that applies.
 - You prefer other sources of information, such as the Summary of Product Information
 - The Guide was too time consuming
 - It is not the first time you prescribed an anticoagulant factor Xa inhibitor, so you did not think the Guide would add to your knowledge

•	Other (please
	specify)

If yes:

- 21. How often have you consulted the Prescriber's Guide thereafter?
 - Never
 - Once
 - 2-3 times
 - More than 3 times
- 22. You find the information in the Prescriber's Guide:
 - Not useful
 - Useful
- 23. Have you referred to other sources of information to aid you in prescribing and managing Lixiana?
 - No
 - Yes, please refer which ones:
- 24. Are you aware of the Patient Alert Card for Lixiana?
 - Yes
 - No
- 25. Have you referred all your patients to the Patient Alert Card, when you first prescribed them Lixiana?
 - a. Yes, always
 - b. Yes, most of the time
 - c. No, not always
 - d. No, I often forget

Card with	them?		
	Yes No		
27. How regularly do you check your patients' knowledge on the content of the Patient Alert Card?			
a.	Never		
b.	In every consultation		
c.	At specific occasions (please specify)		

26. During follow-up consultations, do you confirm if the patient carries the Patient

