Those clinical development programs have been undertaken to support marketing authorisation submissions for edoxaban in those indications. However, as is the case with any medicinal product, real-life use of edoxaban may differ from or extend beyond the patient population that has been studied in the phase 3 program or is included under the approved indication. One of the concerns in real-world use of medicinal practices is the off-label use. Daiichi Sankyo (DS) addressed this concern in the Risk Management Plan (RMP) in order to anticipate necessary risk minimization activities. The potential off-label use of edoxaban in unapproved indications was considered low, because of the availability of approved, indicated and well-established treatment alternatives. However, as it is the case with all other new anticoagulants a residual risk for off-label use might be considered in conditions (for which edoxaban is not approved) that usually also require mid- or long-term anticoagulant treatment or in cases of poor compliance or contraindications of the patient.

Standard routine risk minimisation activities include the communication of the information in the Summary of Product Characteristics (SmPC). In order to further optimise the correct use of the medicinal product by the physician, Daiichi Sankyo Europe GmbH (DSE) is implementing additional risk minimisation activities, namely, prescriber guide as part of the educational programs to make prescribers fully aware of

the approved indications and eligible patients for edoxaban, the dosing recommendations and management of safety concerns. In addition, Patient Alert Cards will be distributed.

The patient alert card is included in every edoxaban package in the European Union (EU).

Furthermore, the DUS, described in this document aims to gain insight on how this new European medicinal product is going to be used in real practice in order to identify prescription patterns, the effectiveness of the educational programs and promptly detect any safety concern, so that pharmacovigilance planning and risk management for edoxaban could be effectively refined, if necessary, on an ongoing basis.

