- o Frequency and distribution of response to each survey question
- Percentage of respondents indicating correct and incorrect responses to each question
- The success/failure rate of the survey (proportion of correct and incorrect answers) overall and by each section (group of related items)
- Assessment of HCPs' opinion/satisfaction on the utility of educational material.

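### Survey Question 25 on the Patient Alert Card has overlapping answer options, so its middle categories and any yes/no reading cannot be interpreted

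*Protocol*

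**What the plan says.** Sections 4 and 7 of the protocol name two additional risk minimisation tools, the Prescriber Guide and the Patient Alert Card. The card is covered by Questions 24 to 27 in Part II of the questionnaire (Appendix 2).

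- Question 24 asks "Are you aware of the Patient Alert Card for Lixiana", yes or no. No skip instruction follows a no.
- Question 25 asks "Have you referred all your patients to the Patient Alert Card, when you first prescribed them Lixiana". Option a is an affirmative meaning always. Option b is "Yes, most of the time". Option c is a negative meaning less than always. Option d is "No, I often forget".
- Question 19 asks "Have you read the Prescriber's Guide". A marker for those who have not read it stands before Question 20, and a marker for those who have stands before Question 21. No later text ends the second branch.

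For the analysis, Section 9.3 lists "Frequency and distribution of response to each survey question" and "Percentage of respondents indicating correct and incorrect responses to each question", both under the assessment of knowledge of the programme's key messages. Section 9.4 has the same survey given again six months later.

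**The concern.** Question 25 sets a universal condition (all patients) and then mixes two scales: a yes/no label and a frequency. Respondents with identical behaviour can therefore give answers with opposite labels, and nothing recorded later tells them apart.

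The chart variables in Section 9.3 contain no card item, so the survey is the study's only source on the card, and Question 25 is its only item on referral at first prescription. A reader of the report would naturally take a and b as doing it and c and d as not doing it. Because the survey is repeated, a drift between b and c could also be mistaken for a change in practice.

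**Working it through.** **1. Which options fit which behaviour (Appendix 2, Question 25)**

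| Physician's actual behaviour | Options that are truthful |
|---|---|
| Refers every patient | a |
| Refers most, not all | b and c |
| Refers some, half or fewer | c; also d if the reason is forgetting |
| Knows the card, never refers | c or d; no option says never |
| Does not know the card (Question 24 = no) | no valid answer |

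Only the first row has an unambiguous answer of its own. Option b carries a yes label although most is not all. Option d is itself a case of c. Option c can hold anyone from nearly always to never.

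**2. What can be recovered.** The split of a against b, c and d together is sound, because only always-referrers fit a. The b/c split is not, because both were true for the same person. Unaware physicians can be separated at analysis through their own answer to Question 24.

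**3. The protocol's own survey figure, for scale.** Section 9.5 assumes 85% with N = 100 and a lower 95% limit above 78%. Wald: 0.85 − 1.96 × √(0.85 × 0.15 / 100) = 0.85 − 0.070 = 0.780. This reproduces the figure. At 50% the half-width is 1.96 × √(0.5 × 0.5 / 100) = 0.098.

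**4. Bound on a yes/no summary of Question 25.** Let A be the share who always refer, s the share who refer most but not all, and k the fraction of the latter who tick b rather than c. Then

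reported yes = A + k × s, with k anywhere from 0 to 1.

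The range is A to A + s with no difference in behaviour. The protocol gives neither A nor s. Assuming A = 50%:

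- s = 10%: 50% to 60%
- s = 20%: 50% to 70%
- s = 30%: 50% to 80%

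These are limits, reached only if every such physician ticks the same option. Between two rounds with unchanged practice, the apparent change is s × (k₂ − k₁).

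**5. Branch before Question 21.** Questions 21 and 22 (how often the Guide was consulted, whether it was useful) depend on having read it. Questions 23 to 27 do not, yet nothing printed returns non-readers to the questionnaire. If the branch were followed to the end, card awareness would be reported for readers only. With r the share of readers, and assuming awareness of 90% in readers and 50% in non-readers:

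all-respondent awareness = 0.90 r + 0.50 (1 − r)

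This is 70%, 78% and 86% for r = 50%, 70% and 90%, against 90% among readers, and the denominator falls from 100 to 50, 70 or 90. All three inputs are assumptions.

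**The case against.** The best defence is that nothing planned depends on a yes/no version of Question 25. Section 9.3 asks for a distribution of responses, and four raw categories can be tabulated. Any collapsing rule belongs to the SAP. Read together, the options look like a descending scale, so a physician who refers 80% of patients has an obvious match in b. No specific objective or precision target concerns referral to the card, and Section 7 says every EU package contains one, so its delivery does not depend on referral. Rewording the item would also disturb the repeat survey.

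Much of this stands. Tabulation is possible, the bound above is a worst case, and the repeat survey must be protected. But an SAP rule can only regroup answers; it cannot separate physicians for whom two answers were equally true. Reading the options as a scale is plausible, but the yes and no labels and the word all in the stem work against it.

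Two stronger readings are tempting and not supported.

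- A reader might infer from Section 9.3 that Question 25 is to be marked correct or incorrect and cannot be. That scoring is listed under knowledge of key messages and fits the Part I items; Question 25 is self-reported practice with no right answer.
- A reader might infer that card awareness is collected only from Guide readers and so is overstated. The unclosed branch may be indentation lost when the file was read, the later questions do not depend on the Guide, and the phone or web form may route correctly. What stands is that the printed text does not say where the branch ends.

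**Conclusion.** The defect is confirmed on the wording, and it concerns Question 25. The options overlap for physicians who refer most but not all patients, never is missing, and physicians unaware of the card have no valid answer. The four counts can be reported and 'always' against the rest can be interpreted; the b/c distinction and any yes/no reading cannot.

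The size is unknown. It is at most the share who refer most but not all patients, and the percentages in the working illustrate this under assumed inputs; they do not estimate the error. Questions 24, 26 and 27 have usable options. The routing is a secondary matter that needs confirmation. Part I knowledge scores, off-label estimates and the sample size are untouched. This is a cheap improvement worth making before the remaining countries are surveyed, and no threat to the study's main results.

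**What to change.** 1. For physicians not yet surveyed (Wave II: Belgium, Italy and Spain from Q3 2017, Portugal from Q1 2018 in Table 5), ask in Question 25 for what share of patients the physician referred to the card at first prescription. Use exclusive options: all, more than half, half or fewer, none. Ask it only if Question 24 is answered yes.
2. Keep the current wording for the six-month repeat of any physician first surveyed with it, so that the comparison within physicians uses one instrument.
3. Across waves, report only all/always against the rest.
4. Confirm how the phone and web forms route respondents after Question 22, and insert a line before Question 23 addressing it and what follows to all respondents, subject to the skip in item 1. Ask Question 24 of every respondent and report it on that denominator.

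The cost is a change of wording and routing in one questionnaire, with two versions of Question 25 in use. The middle categories of Question 25 will not be comparable with Wave I; what is given up is a comparison that the current options could not support.
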